#### Investigational product, dosage and mode of administration:

AXER-204 is a human fusion protein to promote axon growth and recovery of neurological function. AXER-204 is administered by intrathecal lumbar slow bolus injection.

#### Part 1:

Dosage will be by cohort, with 4 sequentially-treated cohorts planned. Intrathecal doses of AXER-204 below 90 mg will be diluted and delivered as a solution in 10 mL of isotonic phosphate buffered saline. Both the 90 mg dose and 200 mg dose will be dosed with the current study drug concentration. All administration will be given following a removal of an equivalent volume of CSF. Intrathecal injections will be given at a rate of 100 mL/hr using a medically approved syringe pump (eg, 12 minutes to administer 20 mL) to avoid significant disruption of natural CSF flow and pressure and monitored by medical personnel.

The starting dose of 3 mg is estimated to be below the pharmacologically active dose. Dose escalation will proceed to 30 mg, 90 mg, 200 mg contingent on safety, tolerability, and available PK. Thus, dosing volumes will be given as follows:

- Cohort 1: 3 mg, 10 mL
- Cohort 2: 30 mg, 10 mL
- Cohort 3: 90 mg, 9 mL
- Cohort 4: 200 mg, 20 mL

#### Part 2

Subject to review of the safety, tolerability, and pharmacokinetic data from Part 1 and DSMB approval, the dose will be 200 mg given once every 3 weeks for 15 weeks as outlined in the schedule of events. Subject to DSMB approval, the dose may be reduced to 90 mg and the dose interval may be modified based on data from Part 1 but is not expected to be less than once every 14 days or more than 28 days. Subject to DSMB approval, the dose and dose frequency may also be adjusted during Part 2 based on emergent safety and tolerability data.

The maximum volume of injection by intrathecal lumbar slow bolus injection is limited to 20 mL in this study based on published tolerance data from studies with other agents employing the same route of administration. If an injection volume of 20 mL, corresponding to a 200 mg dose of AXER-204, is reached in Part 1 dose escalation portion of the study with acceptable safety and tolerance, the 200 mg dose will be designated as the dose for Part 2 at the discretion of the Sponsor in conjunction with the investigators, DSMB, and medical monitor.

#### **Duration of treatment:**

Part 1 is a single-dose treatment for each subject. Subjects will have up to an 84-day screening period, a 3-day in-clinic treatment period, and a follow-up period through 29 days post-dose. Thus, study participation for each subject in Part 1 is expected to be approximately up to 16 weeks in duration.

Part 2 Placebo-controlled Repeat Dose Portion. Subjects will have up to an 84-day screening period, a 104-day treatment period with injections given every 21 days through Day 104, and then post treatment follow-ups at Study Days 137, 169, and 253. The follow-up on Study Day 137 will consist of a telephone call conducted by study personnel to assess status regarding any adverse events. Thus, study participation for each subject in Part 2 is expected to be up to approximately 337 days in duration.

#### Reference therapy, dosage and mode of administration:

Part 1 does not include placebo.

Part 2 includes a matching placebo control, to be given at the same intervals and volume as the investigational product. Placebo consists of a phosphate buffered saline formulation.

At each study site, for each dose to be administered in Part 2, an unblinded pharmacist will prepare prefilled syringes for dose administration in order to maintain the blind for study personnel administering the investigational product and performing all other study procedures.

#### Criteria for evaluation:

#### Pharmacokinetics:

Both serum and cerebrospinal fluid samples will be collected for analyses, as shown in Table 3 and Table 4.

In Part 1, a window relative to the nominal timepoint is allowed for sample collection as follows:

- Blood serum pharmacokinetic samples will be collected at 0 hour (immediately predose), and 1 h (±10 min), 6 h (±10 min), 12 h (±10 min), and 24 h (±10 min) post-dose, as well as at Study Day 4 (72h ± 10 min), 8 (±1d), 15 (±3d), and 29 (±4d).
- Cerebrospinal fluid samples (CSF) will be collected via lumbar puncture at 0 hour (immediately pre-dose), 24 h (±2h) Study Day 4 (72 h ±4h), and Study Days 8 (±1d), and 29 (±4d).

The timing for serum and CSF sample collection may be adjusted for subsequent cohorts based on pharmacokinetic data from the preceding cohorts. Serum PK samples collected at pre-dose and on Study Days 8 and 29 will be analyzed for the presence of anti-drug antibodies (ADA).

In Part 2, Visits 3-7 (Study Days 21, 42, 63, 84, 104) will have a window of  $\pm 5$  days and Visits 8 and 9 (Study Days 169 and 253) will have a window of  $\pm 7$  days. CSF samples will be collected for PK analysis pre-dose on Study Days 1, 21, 42, 63, 84, and 104. The CSF sample collected on Study Day 253 will also be analyzed for PK. Serum samples will be collected for PK analysis pre-dose and 4 h post-dose on Study Days 1, 21, 42, 63, 84, and 104. Serum will also be collected for PK analysis on Study Days 169 and 253. Pre-dose serum will be collected for ADA analysis on Study Days 1, 21, 42, 63, 84, and 104. Serum will also be collected for PK analysis on Study Days 169 and 253. Pre-dose serum will be collected for ADA analysis on Study Days 169 and 253. A subset of the CSF samples may also be analyzed for ADAs depending on development and presence of ADAs in the serum. Part 2 serum and CSF from subjects receiving placebo will be collected but will not be analyzed for PK and ADAs.

In Part 2 on Study Days 1, 21, 42, 63, 84, and 104 a window relative to the nominal timepoint is allowed for sample collection as follows:

- Blood serum pharmacokinetic samples will be collected at 0 hour (within 4 h pre-dose), and 4 h (±10 min) post-dose
- Cerebrospinal fluid samples (CSF) will be collected via lumbar puncture at 0 hour (immediately pre-dose)

#### Table 3:Part 1 Pharmacokinetic Sampling Schedule (Study RNX-AX204-101)

	Day 1 (Dosing day)	Day 2 (24 hours post-dose)	Day 4 (72 hours post-dose)	Day 8	Day 15	Day 29
Cerebrospinal Fluid	Pre-Dose	Х	Х	Х		Х

Serum	Pre-Dose, and post-dose at Hours 1, 6, 12	Х	Х	Х	Х	Х
Serum aliquot for	X (Pre-Dose)			Х		Х

#### Table 4: Part 2 Pharmacokinetic Sampling Schedule (Study RNX-AX204-101)

	Wind	Treatme low at Vis	Follow-Up ± 7 days				
1	21	42	63	84	104	169 M6	253/ET M9
2	3	4	5	6	7	8	9
Х	Х	Х	Х	Х	Х		Х
Х	Х	Х	Х	Х	Х	Х	Х
Х	Х	Х	Х	Х	X	Х	Х
	1 2 X X X X	Wind           1         21           2         3           X         X           X         X           X         X           X         X	Treatment Window at Vis12142234XXXXXXXXX	Treatment Phase Window at Visits 3-7 ± :           1         21         42         63           2         3         4         5           X         X         X         X           X         X         X         X           X         X         X         X           X         X         X         X           X         X         X         X           X         X         X         X           X         X         X         X	Treatment Phase Window at Visits 3-7 ± 5 days           1         21         42         63         84           2         3         4         5         6           X         X         X         X         X           X         X         X         X         X           X         X         X         X         X           X         X         X         X         X           X         X         X         X         X           X         X         X         X         X	Treatment Phase Window at Visits $3-7 \pm 5$ days           1         21         42         63         84         104           2         3         4         5         6         7           X         X         X         X         X         X           X         X         X         X         X         X           X         X         X         X         X         X           X         X         X         X         X         X           X         X         X         X         X         X	$\begin{tabular}{ c c c c c c } \hline & $$Treatment Phase & $$Foll \\ \hline Window at Visits $3-7 \pm 5 days & $$\pm 7$ \\ \hline 1 & $21$ & $42$ & $63$ & $84$ & $104$ & $169$ \\ \hline & $$M6$ & $$M6$ \\ \hline \hline 2 & $3$ & $4$ & $5$ & $6$ & $7$ & $8$ \\ \hline & $X$ & $X$ & $X$ & $X$ & $X$ \\ \hline $X$ & $X$ & $X$ & $X$ & $X$ & $X$ \\ \hline $X$ & $X$ & $X$ & $X$ & $X$ & $X$ \\ \hline $X$ & $X$ & $X$ & $X$ & $X$ & $X$ \\ \hline $X$ & $X$ & $X$ & $X$ & $X$ & $X$ \\ \hline $X$ & $X$ & $X$ & $X$ & $X$ & $X$ \\ \hline $X$ & $X$ & $X$ & $X$ & $X$ & $X$ \\ \hline $X$ & $X$ & $X$ & $X$ & $X$ & $X$ \\ \hline $X$ & $X$ & $X$ & $X$ & $X$ & $X$ \\ \hline $X$ & $X$ & $X$ & $X$ & $X$ & $X$ \\ \hline $X$ & $X$ & $X$ & $X$ & $X$ & $X$ \\ \hline $X$ & $X$ & $X$ & $X$ & $X$ & $X$ \\ \hline $X$ & $X$ & $X$ & $X$ & $X$ & $X$ \\ \hline $X$ & $X$ & $X$ & $X$ & $X$ & $X$ \\ \hline $X$ & $X$ & $X$ & $X$ & $X$ & $X$ & $X$ \\ \hline $X$ & $X$ & $X$ & $X$ & $X$ & $X$ & $X$ \\ \hline $X$ & $X$ & $X$ & $X$ & $X$ & $X$ & $X$ \\ \hline $X$ & $X$ & $X$ & $X$ & $X$ & $X$ & $X$ \\ \hline $X$ & $X$ & $X$ & $X$ & $X$ & $X$ & $X$ \\ \hline $X$ & $X$ \\ \hline $X$ & $X$ & $X$ & $X$ & $X$ & $X$ & $X$ \\ \hline $X$ & $X$ \\ \hline $X$ & $X$ \\ \hline $X$ & $X$ \\ \hline $X$ & $X$ & $X$ & $X$ & $X$ & $X$ & $X$ \\ \hline $X$ & $X$ \\ \hline $X$ & $X$ \\ \hline $X$ & $X$ \\ \hline $X$ & $X$ \\ \hline $X$ & $X$

#### Efficacy

#### Part 1

Part 1 is focused on safety, tolerability, and pharmacokinetics. However, a subset of efficacy assessments are to be performed including:

- ISNCSCI. ISNCSCI is a comprehensive clinician-administered neurological exam for SCI. It is widely used for research and clinical (neurologic) description to fully assess sensory and motor functioning and level of injury in traumatic SCI. The UEMS will be calculated from the ISNCSCI.
- GRASSP. GRASSP is a clinician administered test that assesses strength in 10 key muscles in the upper extremity as well as dexterity and fine motor skills.
- SCIM III self-care and mobility scores. SCIM III measures functional outcomes in three sections: self-care, respiration and sphincter management, and mobility. The current study will employ the self-care and mobility subscores.

#### Part 2

The primary objective of Part 2 is to evaluate the safety, tolerability, and pharmacokinetics of repeat dosing. In addition, a number of efficacy assessments are included as secondary endpoints. The key secondary efficacy endpoint for Part 2 will be within-subject change from pre-treatment baseline and slope for UEMS as compared to placebo. The same trained raters should be used for a particular patient as much as possible. The assessments will be performed in the order outlined in Section 11.2. Additional secondary efficacy endpoints will include within-subject changes from pre-treatment baseline and slope for:

- GRASSP prehension performance scores. GRASSP is a clinician-administered test with three subset scores that assesses strength in 10 key muscles in the upper extremity as well as dexterity and fine motor skills.
- SCIM III self-care scores. Although the SCIM III measures functional outcomes in three sections: self-care, respiration and sphincter management, and mobility, the current study will employ the self-care and mobility subscores. The evaluation will be administered by interview of the patient by a clinician.

Exploratory endpoints will include within-subject changes over time from pre-treatment in:

- ISNCSCI lower extremity motor and sensory scores. ISNCSCI is a comprehensive clinician-administered neurological exam for SCI. It is widely used for research and clinical (neurological) description to fully assess sensory and motor functioning and level of injury in traumatic SCI.
- GRASSP strength, sensation and prehension ability scores
- SCIM III mobility scores
- ISAFSCI. The ISAFSCI will be used to document autonomic control of the heart, blood pressure, sweating, and temperature regulation. Lower urinary tract function, bowel function, and sexual function will be scored.
- Patient Reported Outcomes
  - CUE-Questionnaire (CUE-Q). Assesses subject-reported upper limb function.
  - SF-36 v2. Provides a patient-reported Quality of Life (QoL) assessment. SF-36 will
    provide data on the subjects' perceived health and well-being over the course of the
    study.
  - Neuro-QOL Item Bank v1.0 Upper Extremity Function (Fine Motor, ADL)
  - PGIC Chronic SCI

Exploratory biomarkers of target engagement and axonal growth may be assessed.

#### Safety:

Safety will be evaluated similarly for both Parts, through the collection of data from:

- Physical examinations
- Vital signs
- 12-lead electrocardiograms
- Laboratory parameters (hematology, blood chemistry, and urinalysis). Analysis of CSF for protein, cell count, and glucose.
- Treatment-emergent adverse events (TEAEs).
  - TEAEs will be defined as any AE occurring during or after the injection of study drug or placebo.
  - TEAEs will be limited to those events occurring within 28 days after the last visit.

Condition-specific safety outcomes will include adverse changes in:

- ISNCSCI, GRASSP and all of the neurological measures evaluated for efficacy
- Spasticity (Modified Ashworth Scale). A clinician administered examination for spasticity which measures muscle tone. A score of 0-4 is assigned to each muscle group evaluated. Note: Testing will exclude fingers and thumb.
- Pain (BPI). A self-administered questionnaire used to assess the severity of a subject's pain and the impact of this pain on the subject's daily functioning.

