#### Protocol RNX-AX204-101

Table 5:Part 1 Schedule of Events (Study RNX-AX204-101)1

Study Phase	Screening		In-Clinic	Treat	tment			Post-Treatment Follow-Up			
Study Day	-84	1		2	3	4	5, 6, $7^2$	8	15	29/ET 	
Sound Duy	through -1	Pre-Dose	Post	1 -	•		c , c , .	± 1 days	$\pm 3$ days	$\pm 4$ days	
Visit Number	1	2					Phone Call 	3	4	5	
Informed consents (Main & Biobank)	Х										
Register Subject/Contact EDC/Assign Subject ID	Х										
Inclusion & Exclusion Criteria	Х	X									
Instructions for potential washout period for concomitant medications and for alcohol use	Х										
Urine sample for drug screen 	Х										
Medical/Disease History	Х	Х									
Full Physical Examination & Ht/Wt	Х									Х	
Demographics	Х										
Vital signs (BP, pulse, RR or pulse ox, oral temp) 	Х	Х	Х	Х	Х	Х		Х	Х	Х	
ECG 	Х	Х	Х			Х					
Serum pregnancy, chorionic gonadotropin	Х										
MRI 	Х										
ISNCSCI assessment, including AIS (Clinician Assessed)	Х									Х	
SCIM III self-care and mobility subscores (Clinician Assessed)	Х									Х	
GRASSP (Clinician Assessed)	Х									Х	
Admission/Discharge to/from Clinic		Admit				Discharge					
Physical Examination (abbreviated)		Х				X					
CSF collection (for PK assessment) 		Х		Х		Х		Х		Х	
Dosing of Investigational Product		Dosing									
Study Drug Accountability			Х								
Serum (for PK and ADA assessment) 		Х	Hr 1, 6, 12	Х		Х		Х	Х	Х	
Modified Ashworth Scale (Clinician Assessed)	Х									Х	
SF-36 v2 Health Survey (Subject Reported)	Х									Х	
Neuro-QOL v1.0 – Upper Extremity Function (Fine Motor,	Х									Х	
ADL) (Subject Reported)											
Brief Pain Inventory (Subject Reported)	Х				1					Х	
ISAFSCI (Clinician Assessed)	Х				1					Х	
Clinical laboratory sample collection 	Х	X		Х	Х	X			Х	Х	
Viral Serology 	Х				1					Х	
Urinalysis	Х				1					Х	

Study Phase	Screening		In-Clinic '	Treat	ment		Post-Treatment Follow-Up			
Study Day	-84	1		2	3	4	5, 6, 7 	8	15	29/ET 
	through -1	Pre-Dose	Post				- ) - )	±1 days	± 3 days	± 4 days
Visit Number	1	2					Phone	3	4	5
							Call 			
Urine pregnancy test 		Х								Х
Prior and Concomitant Medications	Prior					Conce	omitant (O	n-going)		
Adverse Events 			Treatment-Emergent (On-going)							
Serious Adverse Events	Pre-		Treatment-Emergent (On-going)							

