<sup>10 Clinical Laboratory Sample Collection: Sample collected on Study Days 1-4 are to be processed locally. INR/PTT is required prior to the Day 1 lumbar puncture procedure with repeat INR/PTT tests on subsequent Study Days at the direction of the Principal Investigator.

<sup>11 Infectious disease testing at Screening and Visit 5 (Study Day 29/ET) will include: HIV-1/HIV-2 antibody, hepatitis B surface antigen, hepatitis C antibody.

<sup>12 Urine Pregnancy Test will be performed locally on site for women of childbearing potential.

<sup>13 Adverse Events are only collected upon the start of study drug. Events occurring prior to this are to be reported as part of the subject medical history. However, SAEs are to be collected from the time of informed consent.

Study Phase	Screening		W	Trea indow a	tment P	hase -7 ± 5 da	vs			Follow-Up ± 7 days	
Study Day	-84 through -1	1	8 (±3 days)	21	42	63	84	104	137 Month 5	169 Month 6	253/ET  Month 9
Visit Number	1	2		3	4	5	6	7		8	9
Informed consents (Main & Biobank)	Х										
Register Subject/Contact EDC/Assign Subject ID	Х										
Inclusion/Exclusion Criteria	Х	Х									
Instructions for potential washout period for concomitant	Х										
medications and for alcohol use											
Demographics	Х										
Medical/Disease History	Х	Х									
Randomization		Х									
MRI 	Х										
Telephone call 			Х						Х		
Full Physical Examination & Ht/Wt	Х										Х
Physical Examination (abbreviated)		Х		Х	Х	Х	Х	Х		Х	
Vital Signs (BP, pulse, RR or Pulse Ox, oral temp) 	Х	Х		Х	Х	Х	Х	Х		Х	Х
ECG 	Х	Х		Х	Х	Х	Х	Х		Х	Х
ISNCSCI assessment including AIS	Х	Х		Х		Х		Х		Х	Х
GRASSP 	Х	Х				Х		Х		Х	Х
SCIM III self-care and mobility subscores		Х				Х		Х		Х	Х
Modified Ashworth Scale		Х								Х	Х
Brief Pain Inventory		Х								Х	Х
Neuro-QOL v1.0 – Upper Extremity Function (Fine Motor, ADL)		Х								Х	Х
SF-36 v2 Health Survey		Х								Х	Х
CUE-Q		Х								Х	Х
PGIC Chronic SCI		Х								Х	Х
ISAFSCI		Х								Х	Х
CSF collection (pre-dose if dosing visit) 		Х		Х	Х	Х	Х	Х			Х
Clinical laboratory sample collection (CSF)		Х		Х	Х	Х	Х	Х			Х
Dosing of Investigational Product		Х		Х	Х	Х	Х	Х			
Investigational Product Accountability		Х		Х	Х	Х	Х	Х			
Serum collection for PK (pre-dose & 4 h post-dose if dosing visit)		Х		Х	Х	Х	Х	Х		Х	Х

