### 11.1.4. Post Treatment Follow-up Visits 3 & 4 (Study Days 8 and 15)

At Visit 3, Study Day 8, subjects' vital signs (BP, pulse, respiratory rate or pulse oximetry, and oral body temperature) will be obtained. Subjects will undergo a lumbar puncture and will have CSF collected for PK assessments. Blood samples will be collected and serum samples for PK assessments and presence of ADA will be obtained. Information on changes or newly administered concomitant medications as well as any new or ongoing AEs will be collected.

Subjects will be given instructions to return to the study site for the next visit and provided an appointment reminder card.

During Visit 4, Study Day 15, blood samples will be collected for clinical laboratory testing and serum samples obtained for PK analysis. Information on changes to ongoing and any new concomitant medication as well as any new or ongoing AEs will be recorded on the eCRF and in the patient's record.

At the completion of the visit, subjects will be given an appointment reminder card that contains the date and time of their next visit to the study site.

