## 14.1. Safety Parameters

Safety will be evaluated similarly for both Parts, through the collection of data from:

- Physical examinations
- Vital signs
- 12-lead electrocardiograms
- Laboratory parameters (hematology, blood chemistry, and urinalysis)
- Treatment-emergent adverse events (TEAEs).
  - TEAEs will be defined as any AE occurring during or after the injection of investigational product.
  - TEAEs will be limited to those events occurring within 28 days after the last visit.

Condition-specific safety outcomes will include:

- ISNCSCI, GRASSP and all of the neurological measures evaluated for efficacy
- Spasticity (Modified Ashworth Scale) [Pandyan 1999]. A clinician administered examination for spasticity which measures muscle tone changes. A score of 0-4 is assigned to each muscle group evaluated (Appendix 5). Notes: Testing will exclude fingers and thumb. Scores are to be recorded for left and right sides for each muscle group tested.
- Pain (BPI) [Cleeland 1994]. A self-administered questionnaire used to assess the severity of a subject's pain and the impact of this pain on the subject's daily functioning.

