### 14.2.3. Adverse Events of Special Interest (AESI)

Adverse Events of Special Interest (AESI) for this study include possible allergic/immune reactions to administration of a protein therapeutic, AEs generally associated with lumbar puncture, and theoretical AEs arising from axon growth. No AESI have been identified from non-clinical toxicology studies with AXER-204. The following are considered AEs of Special Interest for this study:

- Immune/Allergic reactions: fever, rash, arthralgia, myalgia, hematuria, proteinuria, serositis, central nervous system complications, and hemolytic anemia. Injection site reactions may occur
- Events relating to the lumbar puncture procedure: infection, postdural puncture headache, bleeding, brainstem herniation, meningitis, back pain, excessive CSF leakage requiring blood patch
- Complicating infections: discitis and vertebral osteomyelitis
- Neurological symptoms or injuries: low back pain, radicular injury, abducens palsy
- Other: late onset of epidermoid tumors of the thecal sac, increased pain, increased spasticity

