8.8.3 Laboratory Evaluations

All clinical laboratory data will be listed. Data for the following hematology, clinical chemistry, urinalysis and CSF laboratory (part 2 only) analytes (Table 7) will be summarized by dose cohort for Part 1 or treatment group for Part 2 and overall, and by visit. If data for any additional analytes are also recorded, then these will be listed only.

Table 7Clinical Laboratory Tests

Hematology	Clinical Chemistry	Urinalysis	CSF Analysis
			(Part 2)
Hematocrit Hemoglobin Mean corpuscular volume (MCV) Mean corpuscular hemoglobin (MCH) Mean corpuscular hemoglobin concentration (MCHC) Platelet count Red blood cell (RBC) count Red cell distribution width (RDW) White Blood Cell (WBC) Count including differential (neutrophils, lymphocytes, monocytes, eosinophils, basophils)	Alanine transaminase (ALT) Albumin Alkaline phosphatase Aspartate transaminase (AST) Bicarbonate Blood urea nitrogen Calcium Chloride Cholesterol Creatine kinase Creatinine Direct bilirubin Gamma-Glutamyl transferase (GGT) Glucose Lactate dehydrogenase Phosphorus Potassium Sodium Total bilirubin Total bilirubin Total protein Triglycerides Uric acid	Blood Glucose Ketones pH Protein Specific gravity Urine bilirubin	Total protein Glucose Red blood cells count White blood cells count Lymphocytes count Neutrophils count

All laboratory data will be reported in Conventional units. Out-of-reference-range values will be flagged as high (H) or low (L) in the listings.

For analysis purposes, values preceded by a "<" or a ">" sign (i.e. those below or above the limits of quantification) will be considered equal to the lower or upper limit of quantification, respectively.

Hematology and clinical chemistry data will be summarized for each dose cohort using standard descriptive statistics. Changes from baseline will also be summarized. Shift

CONFIDENTIAL

tables presenting movement in and out of reference range from baseline to each scheduled post-baseline visit will also be provided.

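### CSF cell count, protein and glucose are listed as safety tests for the whole study, but Table 5 and the SAP neither schedule nor summarise them for Part 1, which holds the only CSF planned within about a week of a dose

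*Protocol*

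**What the plan says.** Two places include the test for the study as a whole.

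- The safety paragraph of the protocol synopsis opens "Safety will be evaluated similarly for both Parts, through the collection of data from" and includes "Analysis of CSF for protein, cell count, and glucose" among the laboratory parameters.
- Table 12, which section 14.1.5 presents as the laboratory tests for the study, has a CSF block (cell counts, total protein, glucose) and does not restrict it to a Part.

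The other places leave it out of Part 1.

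- Section 14.1 repeats the safety list for both Parts but stops at "Laboratory parameters (hematology, blood chemistry, and urinalysis", with no CSF item.
- Table 5 (Part 1) has one CSF row, "CSF collection (for PK assessment", and no CSF laboratory row. Table 6 (Part 2) has a separate row, "Clinical laboratory sample collection (CSF", and a footnote telling sites to take the CSF laboratory aliquot before other processing.
- Section 11.1.2 assigns the Part 1 pre-dose fluid to PK, biobanking and possibly biomarkers. Section 11.1.4 says of Day 8: "Subjects will undergo a lumbar puncture and will have CSF collected for PK assessments". Section 11.1.5 says the same in substance for Day 29.
- SAP 3.2 omits CSF from the safety variables common to both Parts. SAP 8.8.3 summarises "urinalysis and CSF laboratory (part 2 only) analytes".

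Section 14.1.5 also says that laboratory collection follows Tables 5 and 6. SAP section 9, on departures from the protocol's analyses, does not mention Part 1 CSF.

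**The concern.** A site working from Table 5 would have no instruction to run a test that the synopsis names as part of the safety evaluation. The programmer following SAP 8.8.3 would have no Part 1 CSF table to produce. No reason is given for the difference.

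Protocol section 5.3 describes this study as the first evaluation of the product in humans, and the route is intrathecal. The adverse events of special interest related to the puncture (section 14.2.3) include "infection, postdural puncture headache, bleeding, brainstem herniation, meningitis, back pain", and the immune and allergic group includes central nervous system complications. CSF cell count, protein and glucose bear directly on infection and inflammation in that compartment. If they are not obtained in Part 1, the question is whether Part 2 can supply the same information. That depends on when each Part draws CSF relative to a dose.

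**Working it through.** No power or alpha figure is involved. The check is a comparison of passages plus the dose-to-sample intervals.

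**Does anything in Table 5 restore the test?** Its CSF row carries footnote marker 10, which is also on the clinical laboratory row. Footnote 10 covers local processing of the Day 1 to 4 samples and INR/PTT before the first puncture. It names no CSF analyte. It makes the table ambiguous but does not schedule the test. On Day 8, Table 5 marks no clinical laboratory sample at all, and section 11.1.4 lists only PK and ADA samples for that visit.

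**Part 1 intervals** (synopsis pharmacokinetics text; section 13.2). The dose is on Day 1.

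| Sample | Time after dose | With window |
|---|---|---|
| Day 2 | 24 h | ±2 h |
| Day 4 | 72 h | ±4 h |
| Day 8 | 8 − 1 = 7 days | 6 to 8 days |
| Day 29 | 29 − 1 = 28 days | 24 to 32 days |

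Part 1 enrols up to 24 subjects:

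- draws within about a week of the dose: 24 × 3 = 72 at most
- all post-dose draws: 24 × 4 = 96 at most

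**Part 2 intervals** (same sources). CSF is taken before dosing on Days 1, 21, 42, 63, 84 and 104, and again on Day 253.

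| From dose on | To CSF on | Nominal gap |
|---|---|---|
| Day 1 | Day 21 | 20 days |
| Day 21 | Day 42 | 21 days |
| Day 42 | Day 63 | 21 days |
| Day 63 | Day 84 | 21 days |
| Day 84 | Day 104 | 20 days |
| Day 104 | Day 253 | 149 days |

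Visits 3 to 7 have a window of ±5 days. The shortest gap this allows is (104 − 5) − (84 + 5) = 99 − 89 = 10 days. The last gap ranges over 149 ± (5 + 7), that is 137 to 161 days.

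**Result.** Part 1 has three planned CSF draws at or within about 7 days of a dose. Part 2 has none. Part 2 schedules the safety test but at times that would miss a change that comes and goes in the first days. Part 1 has the right times but does not schedule the test.

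**The case against.** The best case on the other side is that this is a stray synopsis line. Section 14.1, Table 5, the Part 1 procedures and SAP 3.2 and 8.8.3 mostly agree with one another, the synopsis says similar rather than identical evaluation, and section 14.1.5 makes Tables 5 and 6 govern collection. Part 1 also has other safeguards: a 72-hour safety review before the next subject, in-clinic observation to Day 4, frequent vital signs including temperature, advice to suspend the puncture if the fluid is bloody or turbid, and 24-hour reporting of special-interest events. Part 1 has no placebo group and 6 subjects per cohort, so CSF shifts after repeated punctures could not be cleanly attributed to drug.

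Much of this stands, and it limits the point. It does not remove it. Table 12 is body text and sides with the synopsis, so the protocol is at odds with itself outside the synopsis too. The clinical safeguards do not replace a laboratory result, and limited attribution argues for cautious reading of a descriptive cohort summary rather than against having one.

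A reader might infer three stronger things that the documents do not support:

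- **That Part 1 CSF was never checked.** An event-driven work-up is not barred, Table 12 has no Part limit, and SAP 8.8.3 lists all clinical laboratory data. The documents show only that the test is not scheduled or summarised.
- **That Table 5 is the version in error.** The documents conflict but do not say which version was intended.
- **That the results ought to have governed escalation or the DSMB's review before Part 2.** That is a clinical rule for the sponsor. SAP 2.3.2 already reports 23 Part 1 patients evaluated at Day 29, so Part 1 dosing was over when this SAP was written.

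**Conclusion.** The point holds as an unreconciled conflict with a real consequence for the safety data. CSF cell count, protein and glucose are listed for the study in the synopsis and Table 12, but are neither scheduled nor summarised for Part 1 elsewhere. If Table 5 is followed, up to 72 early post-dose draws (96 with Day 29) yield no planned CSF safety result. Part 2 cannot replace them, because its on-treatment samples come nominally 20 or 21 days after a dose and no sooner than 10.

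This rests on the following assumptions:

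- Part 1 enrols its maximum of 24 and keeps the planned sampling times, which the protocol lets the sponsor adjust between cohorts.
- Part 2 keeps the three-weekly schedule and doses are given inside the visit windows. The protocol allows an interval as short as 14 days.
- Unplanned draws are set aside. An early-termination visit in Part 2 includes CSF and could by chance fall soon after a dose.

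**What to change.** Reconcile the synopsis, section 14.1, Table 5, Table 12 and SAP 3.2 and 8.8.3, so that all say the same thing about Part 1.

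- **If the synopsis and Table 12 stand:** add the CSF item to section 14.1 and SAP 3.2. Carry the CSF laboratory row and aliquot footnote of Table 6 into Table 5 at the existing CSF time points (pre-dose, 24 h, 72 h, Day 8, Day 29). Correct or clarify footnote marker 10 on the CSF row. In SAP 8.8.3, remove the Part 2 restriction so that Part 1 results are summarised by dose cohort.
- **If Part 1 samples were not tested:** limit the synopsis and Table 12 to Part 2, and state in the SAP and the study report that no early post-dose CSF safety data were planned.

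Because Part 1 dosing was over when the SAP was written, the practical step is to establish which case applies and to summarise any Part 1 CSF results that exist. Whether such results feed dose escalation or the DSMB review is left to the sponsor.

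The second option costs only text. The first needs no extra puncture. It uses part of each sample, at most 24 × 5 = 120 aliquots including pre-dose, and leaves slightly less fluid for PK, biomarkers or the biobank. The protocol gives a collection volume for the pre-dose draw (roughly 9 to 20 mL) but not for the later Part 1 draws, so the sponsor should confirm that those volumes allow it.
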